**Table 26: Summary of Hematology Tests**

	Biopin 6 1 implant	Biopin 6 2 implants	Placebo 1 to 2 implants
	(N=xx)	(N=xx)	(N=xx)
Repeat for each visit: Screening, Day -1, Day 3, Weeks 4 and 8			
Test Name (units)			
N	xx	xx	xx
Mean (SD)	xx.x (xx.x)	xx.x (xx.x)	xx.x (xx.x)
Min - Max	xx-xx	xx-xx	xx-xx
Change from baseline at Day -1, Day 3, Weeks 4 and 8			
N	xx	xx	xx
Mean (SD)	xx.x (xx.x)	xx.x (xx.x)	xx.x (xx.x)
Min - Max	xx-xx	xx-xx	xx-xx

Programmers note: Hemoglobin, hematocrit, red blood cell count (RBC), reticulocytes, white blood cell count (WBC), and platelets.

**Table 27: Summary of Coagulation Tests at Screening**

	Biopin 6 1 implant	Biopin 6 2 implants	Placebo 1 to 2 implants
	(N=xx)	(N=xx)	(N=xx)
Repeat for each visit: Screening, Day -1, Day 3, Weeks 4 and 8			
Test Name (units)			
N	xx	xx	xx
Mean (SD)	xx.x (xx.x)	xx.x (xx.x)	xx.x (xx.x)
Min - Max	xx-xx	xx-xx	xx-xx

Programmers note: Fibrinogen, prothrombin time (PT), and partial thromboplastin time (PTT).

**Table 28: Summary of Positive Urine Drug Tests**

	Number positive (%)		
	Biopin 6 1 implant	Biopin 6 2 implants	Placebo 1 to 2 implants
Test	(N=xx)	(N=xx)	(N=xx)
Timepoints include: Screening, Day -1, Weeks 4, 8, and 12			
Amphetamine	xx (xx.x%)	xx (xx.x%)	xx (xx.x%)
Barbiturates	xx (xx.x%)	xx (xx.x%)	xx (xx.x%)
Benzodiazapines	xx (xx.x%)	xx (xx.x%)	xx (xx.x%)
Cocaine	xx (xx.x%)	xx (xx.x%)	xx (xx.x%)
Opiates	xx (xx.x%)	xx (xx.x%)	xx (xx.x%)
cannabinoids	xx (xx.x%)	xx (xx.x%)	xx (xx.x%)
phencyclidine	xx (xx.x%)	xx (xx.x%)	xx (xx.x%)
propoxyphene	xx (xx.x%)	xx (xx.x%)	xx (xx.x%)
methadone	xx (xx.x%)	xx (xx.x%)	xx (xx.x%)

**Table 29: Summary of Vital Signs**

	Biopin 6 1 implant	Biopin 6 2 implants	Placebo 1 to 2 implants
	(N=xx)	(N=xx)	(N=xx)
Repeat for each visit: Screening, Day -1, Day 1 predose, then 8, 24, 48, and 72 hours post dose, then Weeks 4 and 8			
Test Name (units)			
N	xx	xx	xx
Mean (SD)	xx.x (xx.x)	xx.x (xx.x)	xx.x (xx.x)
Min - Max	xx-xx	xx-xx	xx-xx
Change from baseline at Day 1 predose, then 8, 24, 48, and 72 hours post dose, then Weeks 4 and 8			
N	xx	xx	xx
Mean (SD)	xx.x (xx.x)	xx.x (xx.x)	xx.x (xx.x)
Min - Max	xx-xx	xx-xx	xx-xx

Programmers note: vital signs include heart rate (sitting), blood pressure (sitting), respiratory rate, oral temperature

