## 2.2 Protocol Timetable

Study Phase	Screening (days -28 to -2)	Day -1	Day 1 to Week 11 	Week 12 (and week 14) 
Informed consent	X			
Demographic data 	X			
Medical history	X	X (update if needed)		
Physical exam 	X	X (update if needed)	Week 4 and 8	X
Weight/height	X			
Urine drugs of abuse screen 	X	X	Week 4 and 8	X
Alcohol breath test	X			
Naloxone challenge test	X	X		
Concomitant medications	X	X	Weekly	X
Serology 	X			
Birth Control Methods/Pregnancy Test 	X	X		
C-SSRS for suicidality	X	X	Weeks 4 and 8	X
HAM-D for depression	X	X	Weeks 2,4,6,8,10	X
Inclusion/exclusion criteria	X	X		
Randomization 		X		
Residential visits		Check in on day (-1)	Check out on Day 4 (72 hours postdose)	Week 12
Non-residential visits	X		Days 7 and 10, and Weeks 2, 3, 4, 5, 6, 7, 8, 9, 10, 11	Week 12 (week 14)
Study drug (Biopin or placebo) administration by implantation			Day 1 (0 h): Insert BIOPIN implant	Remove BIOPIN implant (and week 14) 
Implant Tissue Assessment			At each residential and non-residential visit	Gross and microscopic descriptions and photos of each tissue capsule.

 Age, gender, and race/ethnicity

 Abbreviated (see Protocol Section 8)

 Amphetamines, barbiturates, benzodiazepines, cocaine, opiates, cannabinoids, phencyclidine, propoxyphene, methadone.

 Hepatitis B surface antigen, hepatitis C antibody, human immunodeficiency (HIV-1 and HIV-2) antibodies and p24 antigen, covid antigen

 Serum HCG test at screening; urine HCG test at day (-1). For postmenopausal females, a follicle stimulating hormone test will be performed during screening.

 Each dose cohort of 8 subjects randomized 6 active vs 2 placebo

Study Phase	Screening (days -28 to -2)	Day -1	Day 1 to Week 11 	Week 12 (and week 14) 
Safety and tolerability:				
Adverse event recording	X		Predose, 8, 24, 48 and 72 hours postdose. Then weekly	X
Vital signs 	X		Predose, 8, 24, 48 and 72 hours postdose. Days 7 and 10. Weeks 2, 3, 4, 5, 6, 7, 8, 9, 10, 11	X (pre and post explant)
12-lead ECG	X	X	Week 4 and 8	X (pre and post explant)
Clinical chemistries 	X		72 hours post dose; then weeks 4 and 8	X
Hematology 	X		72 hours post dose; then weeks 4 and 8	X
Coagulation 	X			

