## **8.4 Week 12 and 14: study end**

Subjects will return for a residential visit on week 12 after dosing. Prior to removal, the implant **parameters required by Appendix A** will be assessed (distance from incision, photo of site) as

per after-implantation. At that time, the implant will be removed (Appendix B) and be subject to Gross and microscopic descriptions and photos of each tissue capsule. Blood will be taken for PK pre-explant and 1, 3, 6, 12, 24, 48, 72, 96 hrs after explant. Sampling up to 24 hrs will be as residents; sampling at 48, 72, and 96 hrs (+/- 4 hrs) will be as non-residents. Repeat assessment will be made of adverse effects, vital signs, clinical chemistry, hematology, EKG, concomitant medications, urine drugs, suicidality, depression.

On week 14, 2 weeks after implant removal, the subjects will return for a non-residential visit for surgical evaluation of the implant removal site.

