## Protocol Timetable

Study Phase	Screening (days -28 to -2)	Day -1	Day 1 to Week 11 	Week 12 (and week 14) 
Informed consent	X			
Demographic data 	X			
Medical history	X	X (update if needed)		
Physical exam 	X	X (update if needed)	Week 4 and 8	X
Weight/height	X			
Urine drugs of abuse screen 	X	X	Week 4 and 8	X
Alcohol breath test	X			
Naloxone challenge test	X	X		
Concomitant medications	X	X	Weekly	X
Serology 	X	X		
Birth Control Methods/Pregnancy Test 	X	X		
C-SSRS for suicidality	X	X	Weeks 4 and 8	X
HAM-D for depression	X	X	Weeks 2,4,6,8,10	X
Inclusion/exclusion criteria	X	X		
Randomization 		X		
Residential visits		Check in on day (-1)	Check out on Day 4 (72 hours postdose)	Week 12
Non-residential visits	X		Days 7 and 10, and Weeks 2, 3, 4, 5, 6, 7, 8, 9, 10, 11	Week 12 (week 14)
Study drug (Biopin or placebo) administration by implantation			Day 1 (0 h): Insert BIOPIN implant	Remove BIOPIN implant (and week 14) 
Implant Tissue Assessment			At each residential and non-residential visit	Gross and microscopic descriptions and photos of each tissue capsule.

 Age, gender, and race/ethnicity

 Abbreviated exam

 Amphetamines, barbiturates, benzodiazepines, cocaine, opiates, cannabinoids, phencyclidine, propoxyphene, methadone.

 Hepatitis B surface antigen, hepatitis C antibody, human immunodeficiency (HIV-1 and HIV-2) antibodies and p24 antigen, covid antigen

 Serum HCG test at screening; urine HCG test at day (-1. For postmenopausal females, a follicle stimulating hormone test will be performed during screening.

 Each dose cohort of 8 subjects randomized 6 active vs 2 placebo

Study Phase	Screening (days -28 to -2)	Day -1	Day 1 to Week 11 	Week 12 (and week 14) 
Safety and tolerability:				
Adverse event recording	X		Predose, 8, 24, 48 and 72 hours postdose. Then weekly	X
Vital signs 	X		Predose, 8, 24, 48 and 72 hours postdose. Weeks 4 and 8.	X (pre and post explant)
12-lead ECG	X	X	Week 4 and 8	X (pre and post explant)
Clinical chemistries 	X		72 hours post dose; then weeks 4 and 8	X
Hematology 	X		72 hours post dose; then weeks 4 and 8	X
Coagulation 	X			
Pharmacokinetics (naltrexone and its major metabolite, 6-beta-naltrexol)				

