### 5.2. Safety Endpoints

Safety endpoints will be analyzed over the entire treatment and follow-up period.

1. Adverse events (AEs) and serious adverse events (SAEs)
2. Vital signs
3. Physical examination of the nasal mucosa
4. Blood chemistries and hematology
5. Electrocardiogram (ECG) results
6. Suicidality: Frequency of subjects with suicidal ideation at any time during the treatment period using the Columbia-Suicide Severity Rating Scale (C-SSRS)
7. Depression: HAM-D17 Scores

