**Table 25: Summary of Blood Chemistries**

	Biopin 6 1 implant	Biopin 6 2 implants	Placebo 1 to 2 implants
	(N=xx)	(N=xx)	(N=xx)
Repeat for each visit: Screening, Day -1, Day 3, Weeks 4 and 8			
Test Name (units)			
N	xx	xx	xx
Mean (SD)	xx.x (xx.x)	xx.x (xx.x)	xx.x (xx.x)
Min - Max	xx-xx	xx-xx	xx-xx
Change from baseline at Day -1, Day 3, Weeks 4 and 8			
N	xx	xx	xx
Mean (SD)	xx.x (xx.x)	xx.x (xx.x)	xx.x (xx.x)
Min - Max	xx-xx	xx-xx	xx-xx

Programmers note: table will include alanine aminotransferase, albumin, alkaline phosphatase, aspartate aminotransferase, bilirubin (total and direct), calcium, chloride, cholesterol, creatinine, GGT, glucose, phosphate, potassium, sodium, total protein, uric acid, and BUN.

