**Table 30: Summary of ECG Results**

	Biopin 6 1 implant	Biopin 6 2 implants	Placebo 1 to 2 implants
Result	(N=xx)	(N=xx)	(N=xx)
Screening			
Normal	xx (xx.x%)	xx (xx.x%)	xx (xx.x%)
Abnormal, Not Clinically Significant	xx (xx.x%)	xx (xx.x%)	xx (xx.x%)
Abnormal, Clinically Significant	xx (xx.x%)	xx (xx.x%)	xx (xx.x%)
Other time points include Day -1, Weeks 4 and 8			
Normal	xx (xx.x%)	xx (xx.x%)	xx (xx.x%)
Abnormal, Not Clinically Significant	xx (xx.x%)	xx (xx.x%)	xx (xx.x%)
Abnormal, Clinically Significant	xx (xx.x%)	xx (xx.x%)	xx (xx.x%)

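### SAP Tables 25, 26, 29 and 30 stop at Week 8 and omit the scheduled Week 12 assessments; Table 29 also keeps the vital-sign schedule from before protocol Version 5

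*SAP*

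**What the plan says.** **Protocol.** The timetable in 2.2 gives vital signs from dosing to Week 11 as "Predose, 8, 24, 48 and 72 hours postdose. Days 7 and 10. Weeks 2, 3, 4, 5, 6, 7, 8, 9, 10, 11". Section 8.3 gives the same outpatient visits. For Week 12 the timetable marks vital signs and ECG before and after explant, and chemistry and hematology once. Section 8.4 agrees: "Repeat assessment will be made of adverse effects, vital signs, clinical chemistry, hematology, EKG". The synopsis (2.1, follow-up period) still puts follow-up vital signs at Weeks 4 and 8 only.

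**SAP timetable (4.2).** SAP section 2 says the plan was prepared from protocol Version 5.0. Its vital-sign row nevertheless reads "Predose, 8, 24, 48 and 72 hours postdose. Weeks 4 and 8". Its Week 12 column does mark vital signs and ECG (pre and post explant), chemistry and hematology.

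**SAP shells (13.1.4).** Table 29 (vital signs): "Repeat for each visit: Screening, Day -1, Day 1 predose, then 8, 24, 48, and 72 hours post dose, then Weeks 4 and 8". Table 25 (chemistry), with the same list in Table 26 (hematology): "Repeat for each visit: Screening, Day -1, Day 3, Weeks 4 and 8". Table 30 (ECG), after screening: "Other time points include Day -1, Weeks 4 and 8". The change-from-baseline blocks in Tables 25, 26 and 29 also end at Week 8.

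**SAP text.** The Clinical Laboratory section calls for descriptive statistics at screening and every clinic visit, with change from baseline at every post-randomization visit. The Vital Signs section calls for ECG percentages at every time point. For vital signs it promises summary statistics and change from baseline but names no visits.

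**The concern.** Implants are removed at Week 12, so that visit gives the last assessment with the implant in place. Protocol 5.2 says subjects will be followed for hepatotoxicity, and each dose level has only six active subjects, so one late abnormal value matters. SAP section 2 presents its shells as the outputs to be populated. A programmer who follows these four shells would produce no by-visit group summary of liver enzymes, hematology, vital signs or ECG at the end of exposure. For vital signs, most of the period between Day 4 and explant would be missing too.

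**Working it through.** The plan states no figure to reproduce. The check compares scheduled time points with those in each shell.

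**Inputs.** Schedules come from protocol 2.2, confirmed by 8.3 and 8.4. Shell visits come from SAP Tables 25, 26, 29 and 30. Day 3 in Tables 25 and 26 is read as the 72-hour sample. Pre- and post-explant measurements count as two time points.

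**Step 1: shells against the protocol, post-dose time points only.**

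| Assessment | Scheduled | In shell | Missing |
|---|---|---|---|
| Vital signs | 4 (8, 24, 48, 72 h) + 2 (Days 7, 10) + 10 (Weeks 2 to 11) + 2 (Week 12 pre, post) = 18 | 4 + 2 = 6 | 12 |
| ECG | 2 (Weeks 4, 8) + 2 (Week 12 pre, post) = 4 | 2 | 2 |
| Chemistry | 1 (72 h) + 2 (Weeks 4, 8) + 1 (Week 12) = 4 | 3 | 1 |
| Hematology | 1 + 2 + 1 = 4 | 3 | 1 |

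The protocol has 2 + 10 = 12 outpatient vital-sign visits and Table 29 has 2, so 10 are missing: Days 7 and 10 and Weeks 2, 3, 5, 6, 7, 9, 10 and 11. Adding screening and predose gives 20 scheduled time points, of which Table 29 covers 8. If Week 12 is counted as one visit, the shortfall is 11 of 17 for vital signs and 1 of 3 for ECG.

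**Step 2: Table 29 against the SAP's own timetable.** That timetable has 4 + 2 + 2 = 8 post-dose vital-sign time points. Table 29 has 6, and the missing two are Week 12 pre and post explant.

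**Step 3: separate the two causes.** The older vital-sign row accounts for 12 − 2 = 10 omissions, all outpatient visits. It accounts for none of the Week 12 omissions, because the SAP timetable schedules Week 12 for all four assessments. The Week 12 gap is a separate conflict within the SAP.

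**Step 4: is the SAP timetable really the older one?** The protocol's summary of changes records that Version 5 expanded vital signs from Weeks 4 and 8 and removed Day -1 serology. The SAP timetable still shows both superseded entries, and the current protocol timetable shows neither.

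**Step 5: does the SAP text settle the matter?** For laboratory tests and ECG the text covers Week 12, so shell and text conflict. Protocol 9.2 likewise requires laboratory summaries at every time point in a table. For vital signs no SAP text names the visits, so Table 29 is the only by-visit instruction.

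**The case against.** A reader might infer that the Week 12 data never reach any summary. The documents do not support that:

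- The SAP text requires laboratory statistics at every clinic visit and ECG results at every time point, and the word "include" in Table 30's list can be read as non-exhaustive.
- Protocol 10.6 has clinically significant laboratory results reported as adverse events, and the adverse event tables have no visit limit.
- Figures 1 to 3 plot chemistry, hematology and vital signs over time with no cut-off, and the listings cover all data.
- The SAP plans a summary of vital signs of CTCAE grade 2 or higher that is not restricted by visit.

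These points stand, but they do not close the gap. The graded vital-sign summary has no shell among the 30 tables. The figures show group means and SDs only and include no ECG. Listings are not group summaries.

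It is also tempting to blame the superseded timetable for everything, or to say that the safety shells in general stop early. Step 3 rules out the first. As to the second, Tables 21 to 24 and 28 do include Week 12, which also suggests that the gap is an oversight rather than a choice.

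Two further extensions are not established. Whether the Week 14 check belongs in Table 21 cannot be judged: several of its items concern an implant in place, and the appendices that would define the site parameters are redacted. The Day -1 vital signs in Table 29 may not be simply wrong, because the naloxone challenge records vital signs that day.

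Finally, the study is descriptive, safety is a secondary objective, and no pharmacokinetic output is affected.

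**Conclusion.** The point holds for four shells. Tables 25, 26, 29 and 30 omit Week 12, contrary to protocol 2.2 and 8.4 and the SAP's own timetable, and for laboratory tests and ECG also contrary to the SAP's text. Separately, Table 29 keeps the vital-sign schedule that Version 5 replaced. In size, the shells lack 12 of 18 post-dose vital-sign time points, 2 of 4 ECGs, and the last of 4 chemistry and hematology assessments. The defect is firmest for vital signs, where nothing in the SAP text overrides the shell.

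The loss is from the by-visit tables if these are programmed literally; it is not a loss of data or of every summary. The counts take protocol 2.2 and 8.3 as the reference because the SAP says it follows Version 5.0; the synopsis disagrees for follow-up vital signs. This should be fixed, but it does not threaten the primary analysis.

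**What to change.** 1. Replace the timetable in SAP 4.2 with the one in protocol Version 5.
2. Extend Table 29, including its change-from-baseline block, to Days 7 and 10, Weeks 2 to 11, and Week 12 pre and post explant.
3. Add Week 12 to Tables 25 and 26, including change from baseline.
4. Add Week 12 pre and post explant to Table 30.
5. Reconcile the protocol synopsis on follow-up vital signs with protocol 2.2 and 8.3.

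Minor errata for the same revision: clarify the Day -1 entries in Tables 25, 26 and 29, which the timetable rows for those assessments do not schedule. In SAP 5.2, correct the item "Physical examination of the nasal mucosa", for which the protocol defines no endpoint, and add the incision and implant-site reactions that SAP 4.1.2 names as a secondary objective. The latter are already analysed in SAP 10.5 and 10.7.2.

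The cost is SAP wording, table programming and a protocol clarification. No new assessment is needed, because the protocol already schedules them all. Since SAP section 3 describes the plan as finalized, the change should be documented as a SAP revision or, under protocol 9.5.3, in the clinical study report.

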**Follow up period: Day 3 to Week 11 (non-resident)**

Subjects will return for to clinic for a non-residential visit at the end of each week and also on day 10. The following will be assessed weekly: adverse events, concomitant medications. Blood will be drawn for PK weekly and also on day 10. The following will be assessed at weeks 4 and 8: physical examination, vital signs, urine drugs, suicidality, clinical chemistries, hematology, EKG. Depression will be assessed on weeks 2, 4, 6, 8, 10.

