## **8.3 Weeks 1-to-11 after dosing**

Subjects will return for to clinic for a non-residential visit on day 10 and at the end of each week. The following will be assessed weekly: adverse events, concomitant medications. Blood will be drawn for PK on days 7 and 10 and then weekly. Vital signs will be assessed on Days 7 and 10, and on Weeks 2, 3, 4, 5, 6, 7, 8, 9, 10, 11 The following will be assessed at weeks 4 and 8: physical examination, urine drugs, suicidality, depression, clinical chemistries, hematology, EKG, implant assessment (distance from incision, photo of site) as per after-implantation. For these non-residential visits, acceptable time windows will be the target day +/- 3 days.

**The implant parameters required by Appendix A** will be assessed at each residential and non-residential visit, or if the subject brings it to the attention of the study team. The measures used to prevent complications if they occur are given at the end of Appendix A.

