## **2. INTRODUCTION**

This statistical analysis plan (SAP) for Protocol No. BIOPIN 101, “A Phase 1, placebo-controlled, Single-Ascending-Dose Study of BIOPIN 6 in Healthy Adults” describes and expands upon the analytical plan presented in the protocol.

This document contains all planned analyses, reasons and justifications for these analyses for all study data. This plan also includes sample tables, figures, and listings that will be populated. The SAP will follow the International Conference on Harmonization of Technical Requirements for Registration of Pharmaceuticals for Human Use (ICH) Guidelines as indicated in Topic E3 (Structure and Content of Clinical Study Reports), Topic E8 (General Considerations for Clinical Trials) and Topic E9 (Statistical Principles for Clinical Trials). The structure and content of the SAP provides sufficient detail to meet the requirements identified by the Food and Drug Administration (FDA) and ICH.

The following sources were used in preparation of this SAP:

- Protocol # BIOPIN 101, Protocol Version No.: 5.0; Version Date: 28Jul2024
- ICH Guidance Topics E9, E3 and E8

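### SAP Table 29 tabulates vital signs at only 6 of the protocol's 18 post-dose time points, and its omission of Week 12 contradicts the SAP's own timetable

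*SAP*

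**What the plan says.** **Protocol.** The Timetable in Section 2.2 gives vital signs from Day 1 to Week 11 as "Predose, 8, 24, 48 and 72 hours postdose. Days 7 and 10. Weeks 2, 3, 4, 5, 6, 7, 8, 9, 10, 11". Its Week 12 entry asks for readings on both sides of explantation: "X (pre and post explant". Section 8.3 agrees: "Vital signs will be assessed on Days 7 and 10, and on Weeks 2, 3, 4, 5, 6, 7, 8, 9, 10, 11". Section 8.4 confirms Week 12: "Repeat assessment will be made of adverse effects, vital signs, clinical chemistry". One sentence in the Synopsis, under the follow-up period, differs: "The following will be assessed at weeks 4 and 8: physical examination, vital signs, urine drugs, suicidality, clinical chemistries, hematology, EKG".

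**SAP.** Section 2 names its source as "Protocol # BIOPIN 101, Protocol Version No.: 5.0; Version Date: 28Jul2024". The timetable reproduced in Section 4.2 nevertheless gives "Predose, 8, 24, 48 and 72 hours postdose. Weeks 4 and 8" for Day 1 to Week 11, with Week 12 pre- and post-explant readings in the next column. The Table 29 shell reads "Repeat for each visit: Screening, Day -1, Day 1 predose, then 8, 24, 48, and 72 hours post dose, then Weeks 4 and 8", and its change-from-baseline block stops at Week 8 as well. Section 5.2 lists vital signs among the safety endpoints and says that these are analysed across all of treatment and follow-up. The Vital Signs text (numbered 9.6.3) names no visits. It promises summary statistics, change from baseline, a count of subjects at grade 2 or worse, and listings of every visit.

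**The concern.** A table shell is what the programmer builds. If Table 29 is built as written, blood pressure, heart rate, respiratory rate and temperature will be tabulated through 72 hours, then at Weeks 4 and 8, and nowhere else after dosing. This is a first-in-human study of an implant that stays in place for 12 weeks. The tabulated course would have nothing between 72 hours and Week 4, nothing between Weeks 4 and 8, and nothing after Week 8, which includes the readings around removal. The SAP names vital signs in its secondary objective, and protocol Section 9.2 commits to summary statistics and change from baseline for them. The protocol schedules these visits as routine assessments, and the safety report would be expected to show them.

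**Working it through.** The documents state no total of vital-sign assessments to reproduce, so this is a count of scheduled points. As a check on the counting, the PK row of the same protocol Timetable gives 1 predose + 7 (1 to 72 h) + 2 (Days 7 and 10) + 10 (Weeks 2 to 11) + 9 (Week 12) = 29, which matches the 29 samples stated there.

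Rules: predose is not counted as post-dose. Week 12 pre- and post-explant count as two. Week 14 is described only as a surgical-site visit and is not counted.

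| Post-dose points | Protocol 2.2, 8.3, 8.4 | SAP timetable | SAP Table 29 |
|---|---|---|---|
| 8, 24, 48, 72 h | 4 | 4 | 4 |
| Days 7, 10 | 2 | 0 | 0 |
| Weeks 4, 8 | 2 | 2 | 2 |
| Weeks 2, 3, 5, 6, 7, 9, 10, 11 | 8 | 0 | 0 |
| Week 12 pre, post explant | 2 | 2 | 0 |
| **Total** | **18** | **8** | **6** |

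- Missing from Table 29: 18 − 6 = 12, and 12/18 = 67%.
- Missing from the SAP timetable: 18 − 8 = 10.
- Missing from Table 29 but present in the SAP timetable: 12 − 10 = 2, both at Week 12.
- With the implant in place after 72 h: 2 + 10 + 1 (pre-explant) = 13 scheduled, of which Table 29 shows 2.

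**Sensitivity to the counting rule.** With Week 12 counted once, Table 29 lacks 11 of 17 (65%). On the SAP timetable's own reduced schedule it still lacks 2 of 8.

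**Likely origin.** The protocol's Summary of Changes records that Version 5 expanded vital signs from Weeks 4 and 8 and removed Day −1 serology. The SAP timetable still has the reduced vital-sign row and still marks Day −1 serology. Both fit a timetable carried over from before Version 5. This only explains the cause; the conflict itself is between the current SAP and the current protocol.

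**The case against.** The best case for leaving the plan alone is that little is lost. All visits appear in the listings. The Vital Signs text restricts neither the summary statistics nor the grade 2 or greater count to particular visits. Figure 3 plots mean vital signs over time and names no visits. Under protocol Section 10.6, graded vital-sign abnormalities feed the progression rules whatever Table 29 contains. The study tests no hypotheses, its primary endpoint is PK, and each dose level has six active subjects.

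Most of this stands, and it limits the size of the point. It does not remove it. The grade 2 or greater count has no shell in the SAP's list of tables, so Table 29 is the only specified vital-sign table, and it is narrower than the text it implements.

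A reader might infer more than the documents support:

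- *That the SAP timetable drops all 12 points.* It drops 10. It includes both Week 12 readings.
- *That a site following the Synopsis would not collect the missing readings.* The Synopsis itself lists vital signs at Week 12, and the full Timetable is Section 2.2 of the same Synopsis. One sentence is out of step; no loss of collection is shown.
- *That Figure 3 is also cut to the reduced schedule.* It names no visits, so it is unspecified, not restricted.
- *That the first two weeks after surgery go unsummarised.* The 8, 24, 48 and 72 h readings are in Table 29. What is missing from that period is Days 7 and 10 and Week 2.

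**Conclusion.** The point holds. Table 29 omits 12 of 18 scheduled post-dose points (11 of 17 with Week 12 counted once). Ten follow the outdated row in the SAP timetable. Two are an independent omission that contradicts both that timetable and SAP Section 5.2. The loss is confined to the by-visit tabulated values and change from baseline; the individual readings remain in the listings. I rate it moderate: a safety-summary alignment error with no effect on the primary PK analysis, the analysis sets or the progression rules. Treating it as a threat to the trial's conclusions would go beyond the documents.

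The verdict assumes that the protocol supplied is the version 5.0 that the SAP cites. The SAP dates that version 28Jul2024 and the protocol's Summary of Changes dates it 28Jun2024; the version number agrees, and nothing here depends on the date. It also assumes that readings were taken as Section 8.3 sets out. If some subjects were followed under a shorter schedule, which the documents do not say, the N in each added row would show it.

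**What to change.** 1. Replace the vital-sign row of the SAP timetable with the row in the current protocol Timetable.
2. Extend both blocks of Table 29 (values and change from baseline) to Days 7 and 10, Weeks 2 to 11, and Week 12 pre- and post-explant: 18 post-dose points in place of 6.
3. State in the Figure 3 shell that it uses the same visits.
4. Reconcile the Synopsis follow-up sentence with the protocol Timetable and Section 8.3.

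The cost is edits to one timetable row, one table shell and one figure note in the SAP, plus one sentence in the protocol. No additional data are needed under Section 8.3, and no change to the visit schedule is proposed.
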